6.1.1.3 AMG 330 Outpatient Dosing

Apart from the situations where inpatient dosing is required per [Section 6.1.1.1.2](#), and if deemed stable by the investigator, a subject may continue AMG 330 clV infusion as an outpatient. Subjects will receive a patient card indicating that the subject is participating in a clinical study. The patient card will also provide site contact details to be used in case of questions on the study or an emergency. In the outpatient setting, the subject will either return to the study site for infusion bag changes or the subject will be visited by a well-trained home health care service provider at specific intervals to change the infusion bag, measure vital signs, monitor and document adverse events and/or serious adverse events, and document any issues with the clV infusion or infusion pump. The subject and home health care service provider will be trained and will receive written instructions for storage of the IV bags, if applicable. The home health care service provider will complete the study delegation log and will be authorized by the investigator before any study-related tasks are started.

Refer to the home health care manual for detailed information on the storage, handling, and administration of AMG 330, mandatory procedures, and data collection requirements.

Following each visit or telephone contact by the home health care service provider, the information collected will be documented on the Home Health Care Services visit worksheet and forwarded to the investigator. Any unexpected or unusual events as well as any deviations will be communicated promptly to the investigator. If any adverse event occurs in the outpatient setting, the home health care service provider should directly contact the site for further management. The home health care service professionals provide 24 hour emergency on-call service for any pump related issues. In the event of an interruption of the AMG 330 clV infusion of > 4 hours, restart of the infusion should be performed in the clinic/hospital under the supervision of the

investigator or designee and the subject should be hospitalized for a minimum of 48 hours (see [Section 6.2.2.1](#)).

6.1.1.4 Pembrolizumab Dosage, Administration, and Schedule

Trial treatment should begin as close as possible to the date on which the subject is allocated/assigned. The pembrolizumab treatment to be used in this study is outlined below in [Table 6-2](#).

Schedule of pembrolizumab dosing and related assessments are specified in the Schedule of Activities ([Table 1-1](#), [Table 1-3](#), [Table 1-5](#)). Pembrolizumab will be administered as a dose of 200 mg using a 30-minute IV infusion. Sites should make every effort to target infusion timing to be as close to 30 minutes as possible. However, given the variability of infusion pumps from site to site, a window between - 5 minutes and + 10 minutes is permitted (ie, infusion time is 30 minutes - 5 minutes/+ 10 minutes). Following the completion of the pembrolizumab administration, the subject will be observed for 1 hour to monitor tolerability of the infusion.

For this study, an overdose of pembrolizumab will be defined as ≥ 1000 mg (≥ 5 times the indicated dose) of pembrolizumab. No specific information is available on the treatment of overdose of pembrolizumab. In the event of overdose of pembrolizumab, the subject should be observed closely for signs of toxicity. Appropriate supportive treatment should be provided if clinically indicated.

Table 6-2. Trial Treatment

Drug	Dose/ Potency	Dose Frequency	Maximum Length of Dosing	Route of Administration	Regimen ^a	Use
Pembrolizumab	200 mg	Every 21 days	Up to 35 cycles	Intravenous	Day 1 of each cycle. Starting at study day 15 (cohort 1), and study day 1 (cohort 2) (21-day cycles)	Experimental

^aPembrolizumab may be administered up to 3 days before or after each scheduled day 1 from pembrolizumab cycle 2 onwards.

When pembrolizumab administration falls on the same day as an AMG 330 dose level increase, pembrolizumab will be given first. After the pembrolizumab infusion is

complete, dexamethasone will be administered. The patient will then be observed for 1 hour. If the dose is well tolerated, the dose of AMG 330 may be increased to the next level. When pembrolizumab is administered as a monotherapy, dexamethasone will not be administered at the completion of the pembrolizumab infusion.

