2.3 Benefit/Risk Assessment

As of 17 June 2019, 49 patients have received AMG 330 in the ongoing first in human study. Based on the mode of action targeting CD33 which is expressed on myeloid cells, myelosuppression and particularly neutropenia is expected. In addition, infections may be observed based on the myelosuppressive effect. Neutropenia and infections are conditions that are not unexpected in the setting of AML given the nature of this bone marrow disease.

Cytokine release syndrome (CRS) is an identified risk for AMG 330 and respective signs and symptoms were observed in 67% of subjects treated in the study so far.

Checkpoint inhibition may potentially increase the risk for increased frequency and severity of CRS. This risk is mitigated by the requirement for the administration of dexamethasone prior to each step dose of AMG 330. In addition, in cycle 1 of cohort 1, pembrolizumab is introduced 7 days following the step dose of AMG 330 which may reduce the likelihood or severity of CRS. Lastly, treatment with both dexamethasone and tocilizumab will be available for the treatment of clinically significant CRS.

Pembrolizumab has an acceptable clinical safety profile, is indicated for the treatment of patients across a number of malignancies and is in clinical development as an IV immunotherapy for additional advanced tumors. In patients with a history of allogeneic hematopoietic stem cell transplantation (HSCT), acute Graft versus Host Disease (GVHD), including fatal GVHD, has been reported after treatment with pembrolizumab. Based on the benefit of pembrolizumab treatment vs the risk of GVHD assessment, subjects undergone allogenic HSCT within 5 years prior to the study will be excluded.

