4.1.1 Cohort 1 Design

Cycle 1 is 77 days in duration and subsequent cycles are 57 days. Treatment will start with AMG 330 on day 1. Dexamethasone 8 mg will be given to subjects 1 hour prior to each step dose of AMG 330. AMG 330 will be administered at a starting dose of [REDACTED] µg/day for 3 days, followed by [REDACTED] µg/day for 4 days, followed by [REDACTED] µg/day for 7 days. If the subject experiences DLT during these first 7 days of treatment with AMG 330 at [REDACTED] µg/day, this subject will be replaced. If the subject has not experienced a DLT by day 14, they will receive pembrolizumab on day 15. Pembrolizumab will be administered at a dose of 200 mg (Q3W) by a 30-minute IV infusion. The subject will remain at an AMG 330 dose level of [REDACTED] µg/day for additional 7 days.

Thereafter, AMG 330 dosing will continue as per [Table 4-1](#), increasing dose levels to [REDACTED] µg/day for 7 days followed by [REDACTED] µg/day for 7 days. If the subject has not experienced a DLT at the [REDACTED] µg/day dose level of AMG 330 between days 29 to 35, they will receive pembrolizumab on day 36 and remain on the AMG 330 [REDACTED] µg/day dose for an additional 7 days. AMG 330 dosing will further increase to [REDACTED] µg/day for 7 days followed by [REDACTED] µg/day for 7 days. If the subject has not experienced a DLT at

the █ µg/day dose level of AMG 330 between days █ to █, they will receive pembrolizumab on day 57 and remain on the █ µg/day dose for additional 7 days. To complete cycle 1, a final dose level increase to █ µg/day AMG 330 for an additional 14 days will be administered.

Cycle 1 will be followed by a 1-week interval without AMG 330 administration and administration of pembrolizumab will continue non-interrupted on the Q3W schedule.

The AMG 330-infusion free interval may be extended up to 4 weeks (depending on safety, treatment response, and in case of prolonged marrow aplasia and cytopenia in aleukemic subjects) after consultation with the sponsor.

Table 4-1. Dosing for Cohort 1 (Cycle 1)

AMG 330 Dose Level (µg/day, cIV)	AMG 330 Days Administered	Pembrolizumab Days Administered (IV infusion)
█	D1-3	
	D4-7	
	D8-14, D15-21	D15
	D22-28	
	D29-35; D36-42	D36
	D43-49	
	D50-56; D57-63	D57
	D64-77	
(infusion-free period)	D78-85	D78

cIV = continuous intravenous; D = day; IV = intravenous

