4.3 Justification for Investigational Product Dose

Justification for AMG 330 Dose

The planned dosing schedule for AMG 330 will evaluate doses that have been tested in the ongoing first-in-human study (Amgen Study 20120252) in subjects with R/R AML.

Planned dose levels for step dose escalation will be as follows: [REDACTED]

[REDACTED] and [REDACTED] µg/day. The rationale for selecting these dose levels for the combination study includes following findings generated during the phase 1 dose escalation study: each of the proposed doses has been tested as a monotherapy and deemed safe and tolerable, and proposed dose levels include efficacious doses (CR/CRI have been reported at [REDACTED] and [REDACTED] µg dose levels).

As of 17 June 2019, treatment-emergent adverse events (TEAEs) were reported for 47 (95.9%) of 49 subjects. Forty subjects (81.6%) had grade ≥ 3 adverse events, 33 subjects (67.3%) had serious adverse events, and 2 subjects (4.1%) had fatal adverse events. Six subjects (12.2%) had adverse events that led to discontinuation of AMG 330. Dose-limiting toxicities (DLTs) were reported for 6 subjects. The most frequently reported adverse event by preferred term was CRS (31 subjects, 63.3%). Adverse events considered by the investigator to be related to AMG 330 were reported for 43 subjects (87.8%), the most frequently reported treatment-related adverse events (subject incidence $\geq 20\%$) were CRS (63.3%), rash (30.6%), febrile neutropenia (22.4%), and nausea (20.4%).

CRS mitigation approach developed for AMG 330 and implemented into the ongoing first in human study allows resolution of CRS within 7 days. Thus, the duration of each step dose is defined as at least 7 days to allow monitoring the frequency, severity and resolution dynamics of CRS in subjects treated with the combination regimen. An exception is given for first 2 lower doses ([REDACTED] µg/day and [REDACTED] µg/day), duration for which will be 3 and 4 days respectively, since the occurrence of CRS is rare at these doses due to the current CRS mitigation approach (ie, premedication with dexamethasone 8 mg 1 hour prior to each step dose of AMG 330).

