Please also refer to specific guidance on restart after CRS in [Section 6.8](#). Restarting the infusion after a treatment interruption requires care. The re-start should be performed in the hospital, under supervision of the investigator or designee, if the reason for the interruption was other than a technical issue or the interruption exceeded 4 hours independent of reason. Assessments should be performed after infusion re-start depending on the length of the interruption. The subject should be hospitalized for at least 48 hours after re-start of the infusion.

In case of an AMG 330 infusion interruption of > 24 hours, regardless of the reason for interruption, re-start of the infusion (repeat cycle) should be performed using step doses, which will be defined upon consultation with the sponsor. Only 2 repeat cycles may be performed in cycle 1. For cycle 2 and beyond, additional repeat cycles can be permitted upon discussion and agreement between the investigator and sponsor.

Step doses will be performed within 1 – 2 weeks (\pm 1 day) to return to the interrupted AMG 330 dose level, and the number and duration of repeat step doses will depend on the level of interrupted AMG 330 dose. During this 1-2 weeks, [Table 1-7 Schedule of Activities](#) should be followed (eg, for AMG 330 doses interrupted at [REDACTED] μ g/day and below, 2 step doses can be used: [REDACTED] μ g/day for 3 days followed by [REDACTED] μ g/day for 4 days; for doses interrupted above [REDACTED] μ g/day, 3 step doses can be used: [REDACTED] μ g/day for 1 day followed by [REDACTED] μ g/day for 3 days followed by [REDACTED] μ g/day for 3 days). In case of AMG 330 infusion interruption for < 24 hours, regardless of the reason for interruption, restart of infusion should be performed at the same dose level as the last dose level. Administration of pembrolizumab will remain on the Q3W schedule.

After 2 unsuccessful restarts, the subject may remain on the study and continue AMG 330 treatment with a previously tested target dose that has been well tolerated. The dose of pembrolizumab will remain unchanged.

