8.1.2 Treatment Period

Visits will occur per the Schedule of Activities ([Table 1-1](#), [Table 1-3](#), [Table 1-5](#)). The date of the first dose of protocol-required therapies (AMG 330 and/or pembrolizumab) is defined as day 1. All subsequent doses and study visits will be scheduled based on the day 1 date. Cycle 1 on-study visits have a \pm 1-day window from designated time point. All subsequent visits beginning in cycle 2 will have a \pm 3-day window.

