## 3.1.1 Cohort 1 Design

Cycle 1 is 77 days in duration and subsequent cycles are 57 days. Treatment will start with AMG 330 on day 1. Dexamethasone 8 mg will be given to subjects 1 hour prior to each step dose of AMG 330. AMG 330 will be administered at a starting dose of µg/day for 3 days, followed by µg/day for 4 days, followed by µg/day for 7 days. If the subject experiences DLT during these first 7 days of treatment with AMG 330 at µg/day, this subject will be replaced. If the subject has not experienced a DLT by day 14, they will receive pembrolizumab on day 15. Pembrolizumab will be administered at a dose of 200 mg (Q3W) by a 30-minute IV infusion. The subject will remain at an AMG 330 dose level of µg/day for additional 7 days.

Thereafter, AMG 330 dosing will continue as per Table 3-1, increasing dose levels to µg/day for 7 days followed by µg/day for 7 days. If the subject has not experienced a DLT at the µg/day dose level of AMG 330 between days 29 to 35, they will receive pembrolizumab on day 36 and remain on the AMG 330 µg/day dose for an additional 7 days. AMG 330 dosing will further increase to µg/day for 7 days followed by µg/day for 7 days. If the subject has not experienced a DLT at the µg/day dose level of AMG 330 between days 50 to 56, they will receive pembrolizumab on day 57 and remain on the µg/day dose for additional 7 days. To complete cycle 1, a final dose level increase to µg/day AMG 330 for an additional 14 days will be administered.

Cycle 1 will be followed by a 1-week interval without AMG 330 administration and administration of pembrolizumab will continue non-interrupted on the Q3W schedule. The AMG 330-infusion free interval may be extended up to 4 weeks (depending on safety, treatment response, and in case of prolonged marrow aplasia and cytopenia in aleukemic subjects) after consultation with the sponsor.

Cycle 2 will start with the initiation of AMG 330 administration and include the same step dose levels and duration as in cycle 1 with the exception of the and pg/day dose levels, which will be shortened from 14 days to 7 days (Table 3-2). The duration of AMG 330 step dose levels in cycle 2 and beyond can be shortened to 2 to 5 days if a subject tolerated the investigational product in cycle 1 and based on the discussion and agreement between the investigator and the sponsor. All subsequent cycles will be conducted similarly to cycle 2.

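### Table 6-2 footnote a lets the cohort 1 day 36 and day 57 pembrolizumab doses be given up to 3 days early, before the 7 DLT-free days that Section 4.1.1 requires are complete

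*Protocol*

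**What the plan says.** Protocol Section 4.1.1 ties the second and third pembrolizumab doses of cohort 1, cycle 1 to a DLT-free week at a newly reached AMG 330 level. For subjects with no DLT at the "dose level of AMG 330 between days 29 to 35, they will receive pembrolizumab on day 36". The same condition applies three weeks later. The day numbers are blacked out in the protocol, but SAP Section 3.1.1 shows them: for subjects with no DLT at the "dose level of AMG 330 between days 50 to 56, they will receive pembrolizumab on day 57".

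Protocol Section 6.1.1.4 sets the pembrolizumab dosing window. The regimen column of Table 6-2 reads "Starting at study day 15 (cohort 1), and study day 1 (cohort 2) (21-day cycles", and footnote a to that column says that pembrolizumab "may be administered up to 3 days before or after each scheduled day 1 from pembrolizumab cycle 2 onwards". The footnote names no exception for cohort 1 and does not mention the DLT condition.

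Protocol Section 8.1.2 has a different tolerance: "Cycle 1 on-study visits have a" ±1-day window, widening to ±3 days from cycle 2. That sentence is about visits. No text says whether it also limits the pembrolizumab dose, or which of the three provisions prevails.

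**The concern.** A stated permission runs against a stated safety condition. A condition that covers days 29 to 35 cannot be confirmed on day 33, yet the footnote allows the dose on that day. The footnote excludes only the first pembrolizumab dose, on day 15, so its early side opens at exactly the two later doses that carry a DLT condition.

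What is at stake is small but concrete. A DLT that first appears on days 33-35 (or 54-56) would not be known when an early dose is given. Some DLT definitions in Section 6.2.1 also run on a clock. For example, a grade 3 or 4 asymptomatic enzyme elevation is excused if it falls to grade 2 or lower within 7 days, so one that starts on day 29 may not yet be classifiable on day 33.

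**Working it through.** **Inputs.** Pembrolizumab starts on study day 15 in cohort 1 and is given in 21-day cycles (Table 6-2). AMG 330 cycle 1 lasts 77 days (Section 4.1.1). The AMG 330 steps in question start on days 29 and 50, and the next steps on days 43 and 64 (Table 4-1). The DLT-free periods are days 29-35 (Section 4.1.1) and 50-56 (SAP Section 3.1.1). The windows are ±3 days (footnote a) and ±1 day (Section 8.1.2, if it applies to dosing).

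**Reproducing the schedule.** The day of pembrolizumab dose k is 15 + 21 × (k − 1), which gives days 15, 36, 57 and 78, as in Table 4-1. As a cross-check on cycle length, 35 × 21 = 735 days, or 2.01 years, which agrees with the protocol's approximate 2 years for 35 cycles. The footnote therefore counts pembrolizumab cycles, not AMG 330 cycles. Its cycles 2 and 3 are days 36 and 57, both inside AMG 330 cycle 1. Day 78 falls in the AMG 330 infusion-free period and carries no such DLT condition.

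**Permitted days.** Footnote a: 36 ± 3 = days 33-39, and 57 ± 3 = days 54-60. Visit window, if it governs: 36 ± 1 = days 35-37, and 57 ± 1 = days 56-58.

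**Completed observation days before the dose** = dose day − first day of the step:

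| Dose day | Completed days | Permitted by |
|---|---|---|
| 33 or 54 | 33 − 29 = 54 − 50 = 4 of 7 | footnote a only |
| 34 or 55 | 5 of 7 | footnote a only |
| 35 or 56 | 6 of 7 | footnote a; visit window if it governs |
| 36 or 57 | 7 of 7 | all provisions |

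For each dose, 3 of the footnote's 7 days come before the condition can be met. If the visit window governs, 1 of its 3 days does. Only days 36-37 and 57-58 satisfy every provision at once.

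**After the fix.** With 0/+3 days the doses fall on days 36-39 and 57-60, and all 7 observation days are complete on every permitted day when the steps start on schedule.

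**The case against.** The strongest reply is that the texts can be read together. Section 4.1.1 sets a specific, subject-level condition; footnote a is a general scheduling tolerance that does not mention DLTs. On the ordinary reading, a tolerance does not waive a safety condition, and a careful site would wait. This largely stands, and it is why the point is minor. But it makes the early side void for these two doses without any text saying so.

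Second, Section 6.1.1.4 refers to the Schedule of Activities for pembrolizumab dosing, and days 36 and 57 are cycle 1 visits. A site that followed both windows could be at most 1 day early. That is plausible, though no precedence is stated, and one day early still leaves the seventh day unobserved.

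Third, other rules limit the harm. Table 6-5 withholds pembrolizumab until CRS is grade 1 or lower, and Section 6.2.1 stops dosing at any DLT and counts DLTs throughout cycle 1. Tables 4-2 and 4-3 schedule pembrolizumab on the same day as an AMG 330 step in later cohort 1 cycles and in cohort 2, so close spacing is not foreign to the plan. All of this stands. These rules act on events already present, however, and do not supply the missing observation days.

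Two stronger readings fail. A reader might infer that early dosing breaches Section 4.3, where "the duration of each step dose is defined as at least 7 days to allow monitoring the frequency, severity and resolution dynamics of CRS". That sentence is about the length of AMG 330 steps, which an early pembrolizumab dose does not shorten: the levels on days 29-42 and 50-63 still last 14 days. A reader might also apply to days 36 and 57 the Section 2.3 statement that "pembrolizumab is introduced 7 days following the step dose of AMG 330 which may reduce the likelihood or severity of CRS". The word for starting the drug most naturally refers to the first dose, on day 15, which the footnote leaves alone.

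**Conclusion.** The conflict is real and minor. Footnote a taken alone allows two of the three conditional pembrolizumab doses in cohort 1, cycle 1 after 4 of 7 observation days; the visit window, if it governs, allows them after 6 of 7. This rests on counting 21-day pembrolizumab cycles from day 15, which Table 6-2 states, and on AMG 330 steps that start on schedule. Days 33 and 54 are permitted extremes, not expected conduct.

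A reader might infer that the cohort 2 decision or the DLT analysis is compromised. The documents do not support that. The decision uses DLTs by day 28, before either dose could be given even at the early limit (day 33), and later cycle 1 DLTs still count. No endpoint, estimate or analysis set changes.

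**What to change.** Amend footnote a so that the cohort 1, cycle 1 doses on days 36 and 57 have a window of 0/+3 days and are given only after the 7-day DLT-free period at the current AMG 330 step is complete. Add a sentence to Section 8.1.2 saying that this window, not the visit window, governs these two doses.

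The cost is one footnote and one sentence in an amendment. Sites lose the option of dosing on days 33-35 and 54-56. The late side stays as it is: a dose on day 39 or 60 leaves 43 − 39 = 64 − 60 = 4 days before the next AMG 330 step, against 7 on schedule, which footnote a already allows.

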6.1.2 Non-investigational Products

There are no non-investigational products in this study.

6.1.3 Medical Devices

AMG 330 must be administered using infusion pumps approved for use by the appropriate regulatory authorities for the country in which the subject is undergoing treatment in both the inpatient and outpatient setting. Investigational product infusion for solution will be prepared in bags for IV infusion and delivered through infusion lines with a 0.2 µm in-line filter that are both compatible with the investigational product as described in the IPIM.

Additional details are provided in the IPIM.

Other non-investigational medical devices may be used in the conduct of this study as part of standard care.

Non-investigational medical devices (eg, syringes, sterile needles), that are commercially available are not usually provided or reimbursed by Amgen (except, for example, if required by local regulation). The investigator will be responsible for obtaining supplies of these devices.

